4.5 Power Estimate

The primary intention to treat population will include all participants randomized. The effect size of pioglitazone is estimated based on studies. Schmitz et al found a small effect size favoring pioglitazone (94% likelihood of decrease in alcohol use versus 83% in placebo) which is likely low as all the subjects studied had a primary cocaine use disorder diagnosis with an AUD secondary. Based on a sample of Veterans at the Minneapolis VAHCS who had taken

pioglitazone during fiscal year 2016 we found that taking pioglitazone was associated with decreased alcohol use as measured by the AUDIT-C with an effect size of $d=.48$.

Using G*power we estimated sample size for various base rates of drinking (heavy drinking days per week) by various differences in reductions in rate produced by pioglitazone versus placebo across the 14 weeks follow-up period using Poisson regression. Baseline heavy drinking days per week in our Baclofen study, was 3.5 per week. Based on this we estimate that we are adequately powered to find clinically meaningful differences in reduction (20% or greater) given our proposed sample size.

Base Rate per week (Heavy Drinking Days)	Reduction in rate.	Power	Total N
4	19%	80%	164
3	19%	80%	217
2	19%	80%	321
4	20%	80%	147
3	20%	80%	194
2	20%	80%	288
4	21%	80%	132
3	21%	80%	175
2	21%	80%	260
4	22%	80%	120
3	22%	80%	159
2	22%	80%	235
4	23%	80%	109
3	23%	80%	145
2	23%	80%	214

Thus, we feel that the sample size of 200 (100 per site) is still warranted.

For **secondary outcomes** including the categorical outcome (no heavy drinking days in the last 8 weeks of the study) with 90 patients in each group (100 recruited subjects in each group, assuming 20% attrition) we estimate that this sample size will allow us to find a 22% difference (OR=2.45) in heavy drinking days with 80% power at $p<.05$. Both mixed models and GEE allow us to take full advantage of the ITT sample and thus power is based on 90 subjects per group. Other secondary measures including biomarkers of alcohol use (EtG/EtS and GGT) and for craving we will use linear mixed models to compare change in biomarkers and change in OCDS scores. Estimates for comparisons of these continuously distributed outcomes indicate

that we will be able to find effect sizes of $d=.47$ with 72 subjects or larger with 100 subjects per group.

4.6 Attrition: We anticipate an attrition rate of 20% and this has been considered when calculating the budget and in the power analysis. Rationale for this estimate includes several factors. The attrition rate in our prior studies ranged from 14% (55) to 24% (34). Second, some patients may be more interested in remaining in a medication study with high perceived efficacy. The medication will be dispensed at the outpatient clinic, which should reduce the stigma typically associated with specialty alcohol treatment. Finally, participant compensation will provide an incentive to complete the follow-up sessions. However, we have reviewed other VA alcohol treatment studies that showed great variation in attrition rates, **therefore we are projecting a conservative estimate that 80% of the participants consented will complete the study.**

4.7 Missing Data: We will perform an intent-to-treat analysis, meaning that all subjects randomized into two treatment groups will be included in the analysis regardless of the extent of compliance with the treatment or withdrawals during the trial. This will create incomplete data because some subjects will withdraw from the study during the course of the treatment, thereby their responses will be considered missing after withdrawal. **If the dropout process is related to the outcome measures (i.e., alcohol use), this will present a challenge in the analysis.** The majority of the currently available statistical methods assume that data are missing at random. However, in this study, it is plausible that the likelihood of dropout is related to the level of or change in alcohol use. For example, those with increase or no reduction in alcohol use may be more likely to drop out of the study. When subjects drop out of the study, we will attempt to obtain data on reasons for dropout. We will analyze whether the dropout process is at random with respect to the outcome measures. If the dropout process is related to the outcome measures, we will utilize models that incorporate a nonrandom dropout mechanism (Little, 1995). These analyses will be carried out as the secondary analyses for hypothesis-generating purposes. Use of the EM algorithm in the analysis will allow inclusion of observations with missing datapoints. This increases power and improves the ability to produce estimates with less bias.

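### Section 4.5's power statement contradicts its own attrition figure (90 per group where 20% loss leaves 80), and its primary table cannot be reproduced without settings the plan does not state

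*Combined protocol and SAP*

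**What the plan says.** **Primary outcome (section 4.5).** A table of 15 total sample sizes, 109 to 321, is labelled 80% power for 19-23% reductions at 2, 3 or 4 heavy drinking days per week. The rate differences are those "produced by pioglitazone versus placebo across the 14 weeks follow-up period using Poisson regression". The planning rate is "Baseline heavy drinking days per week in our Baclofen study, was 3.5 per week", and the conclusion is that "we are adequately powered to find clinically meaningful differences in reduction (20% or greater) given our proposed sample size". The proposed size is 200.

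**Secondary outcomes (section 4.5).** The responder comparison is powered "with 90 patients in each group (100 recruited subjects in each group, assuming 20% attrition"), and "this sample size will allow us to find a 22% difference (OR=2.45) in heavy drinking days with 80% power" is claimed. The reason offered is that mixed models and GEE use the whole intention-to-treat sample, "thus power is based on 90 subjects per group". For biomarkers and craving, d=.47 is said to be detectable "with 72 subjects or larger with 100 subjects per group".

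**Elsewhere.** Section 4.6 repeats 20% attrition, projects 80% completion, and reports that "The attrition rate in our prior studies ranged from 14% (55) to 24% (34"). Section 4.4 tests the responder outcome by chi-square and analyses the continuous outcomes by mixed models or GEE. It gives p < 0.05 for categorical outcomes and does not mention tails.

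**The concern.** A power statement should let a reader recover its result from its inputs. Here one input is arithmetically wrong. Others are missing: tails, the primary alpha, the exposure entered, overdispersion and within-patient correlation. The exposure the table appears to use differs from the 14 weeks described. The 3.5 per week is a baseline rate, whereas the contrast is between arms on study.

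At stake is whether 200 patients carry a reserve against the expected 20% loss. Interpolating the table at 3.5 per week and 20% gives about 167 patients (147 x 4 = 588 and 194 x 3 = 582; mean 585; 585/3.5 = 167), which looks like 33 to spare. Whether that reserve exists depends on the unstated settings.

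**Working it through.** **1. Attrition.** 100 x (1 - 0.20) = 80 per group. Ninety means 10% attrition, below both of the sponsor's prior trials: 14% would leave 86, and 24% (the baclofen trial, which also supplies the 3.5 per week) would leave 76. Using the full intention-to-treat sample would argue for 100, not 90, and does not apply to a chi-square test on responders.

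**2. Responder test.** Take 39% v 61%: a 22-point gap with OR (0.61/0.39)^2 = 2.45. The rates are an assumption, since the plan gives only the gap and the OR. Two-sided 5%:

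power = Phi{[0.22 - c - 1.96 sqrt(2 x 0.25/n)] / sqrt[(0.39 x 0.61 + 0.61 x 0.39)/n]}, with c = 0 uncorrected or 1/n continuity-corrected.

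| n per group | Uncorrected | Corrected |
|---|---|---|
| 80 | 80.1% | 75.2% |
| 90 | 84.5% | 80.6% |

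The plan's 80% can be reached from 80 uncorrected or from 90 corrected.

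**3. The d=.47 figure.** A two-sided 5% t-test with 72 per group gives 80.0% at d=.47, so this figure reproduces, but on a third sample size. Detectable d is .45 at 80, .42 at 90 and .40 at 100 per group.

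**4. Primary table.** Two-group Poisson, 1:1, base rate b as the placebo rate, t weeks of exposure, rate ratio RR, Wald test of log RR:

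N = (z_alpha + z_0.80)^2 x (2 + 2/RR) / (b t [ln RR]^2).

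For RR = 0.80, 2 + 2/RR = 4.5 and (ln RR)^2 = 0.0498. The squared z-sum is 6.18 one-sided and 7.85 two-sided at 5%.

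| Base rate | Printed N | One-sided, t=1 | Two-sided, t=1 | Two-sided, t=14 |
|---|---|---|---|---|
| 4 | 147 | 139.7 | 177.3 | 12.7 |
| 3 | 194 | 186.2 | 236.4 | 16.9 |
| 2 | 288 | 279.4 | 354.7 | 25.3 |

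Fourteen weeks of plain Poisson exposure would need about 13-25 patients, so the printed values were not obtained that way.

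Across all 15 rows:
- one-sided, t = 1.00: printed N is 3-5% above the formula;
- one-sided, t = 0.96: within 1.3%;
- two-sided, t = 1.22: within 1.3%.

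The table fixes only (z_alpha + z_beta)^2/t. It cannot separate one-sided from two-sided.

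**5. Power if t = 1 and the test is two-sided 5%.** Two variance forms:
- Wald: Phi(|ln RR| sqrt[N b/(2 + 2/RR)] - 1.96);
- null variance from the control rate: Phi{[|ln RR| sqrt(N) - 1.96 sqrt(4/b)] / sqrt[(2 + 2/RR)/b]}.

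| Setting | Wald | Control-rate null |
|---|---|---|
| The 15 printed Ns | 71.3-72.3% | 74.9-76.3% |
| N=200, 3.5/week, 20% | 79.5% | 82.5% |
| N=180 | 75.2% | 78.6% |
| N=160 | 70.2% | 73.9% |

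The N for 80% at 3.5 per week is 203 (Wald) or 187 (control-rate null), against the 167 the table implies.

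**6. Spread (illustration only; the documents give no variance).** Assume 14 weekly counts at 3.5 per week and a between-patient variance of the relative rate k. The variance of the log rate ratio is then [2/(14 x 3.5) + 2/(14 x 3.5 x 0.80) + 4k]/N. With N=200 and RR=0.80, two-sided, k = 0.10, 0.25 and 0.50 give 99%, 86% and 59%. In such an analysis the omitted quantity decides the power.

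**The case against.** The strongest reply is that the quoted sentence concerns 200 patients at 3.5 per week, where even a two-sided one-week model gives about 80-83%. That stands: the adequacy claim roughly holds if all 200 contribute fully. It also stands that mixed models and GEE keep partial data, so 70-74% at 160 is a worst case rather than an expectation. Section 4.4's wording suggests 0.05 for the primary outcome too, though it says nothing of tails. The 3.5 is openly labelled as baseline, and rates of 2, 3 and 4 are tabulated.

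A reader might infer more than the documents support:

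- **That the table is one-sided and the trial has only 71-72% power.** This requires fixing exposure at exactly one week and using one variance form. A two-sided test with about 1.22 weeks fits the table as well. The 71-76% range applies to the printed Ns under the one-week, two-sided assumption, not to the planned 200.
- **That the 90 v 80 slip defeats the responder claim, or that 80 was the number really used.** An uncorrected chi-square at 80 still gives 80.1%, and a corrected one at 90 gives 80.6%. The plan does not say which was run.

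None of this removes the attrition contradiction, the mismatch between 14 weeks and the printed Ns, or the missing settings.

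**Conclusion.** The point holds as one of internal inconsistency and missing inputs, not as proof that the trial is underpowered. Ninety per group is wrong under the plan's own 20% attrition, and three different numbers (90, 72 and 100) appear where one should. With 80 per group the responder power is 80.1% or 75.2%, depending on an undeclared continuity correction and on assumed rates near 39% v 61%.

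The primary table rests on about one week of exposure and no between-patient spread, which does not match the 14-week repeated-measures analysis. Two-sided with one week, the planned 200 give about 80-83% at 3.5 per week and a 20% reduction. This assumes that the on-study placebo rate equals the baseline rate and that everyone contributes fully. True power for the mixed model or GEE could be higher or lower and cannot be determined from the documents. The point should be fixed, but it does not call the sample size into question.

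**What to change.** Keep N=200.

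- **Secondary outcomes:** replace 90 with 80 per group for the responder test, state whether the chi-square is continuity-corrected, and restate the detectable difference. Use one reconciled number in all secondary power statements; at 80 per group the detectable d is .45.
- **Primary outcome:** declare two-sided alpha 0.05. Recompute the table with the exposure per patient, overdispersion and within-patient correlation stated, so that it matches the planned mixed model or GEE. Take the on-treatment placebo rate and variance from the sponsor's own baclofen trial. Then restate the detectable reduction in place of the present adequacy sentence.

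The cost is protocol and SAP wording plus one recalculation from data that the sponsor should already hold. No extra patients and no change of endpoint or analysis are needed. The downside is that a stated figure may become slightly less favourable.

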4.4 Primary and secondary outcome measures

For the primary outcome we will use change in number of heavy drinking days per week. Secondary outcome measures will include a responder analysis, the rate of no heavy drinking over the last 8 weeks of the study, and another continuous measure of alcohol use including number of drinks per week over the entire study period. Heavy drinking days per week was chosen as it is a standard outcome used previously used in clinical AUD trials (34, 55). The responder analysis measure of no heavy drinking days over the last 8 weeks of the active study period (weeks 6-14) was chosen as a secondary outcome as it was recently recommended by the FDA in their guidance to industry for the development of drugs for alcoholism (35). The FDA report indicated that a responder analysis is preferable to analysis of group means as mean differences are difficult to interpret with regard to clinical relevance. In addition, changes in this measure is associated with good clinical outcomes (35). Each subject will be assessed for the outcome variables (alcohol consumption) at baseline (date of randomization), 1,2,3,4,6,8,10,12 and 14 weeks (week 16 is a safety check as medications will be tapered off starting at week 14). For the responder analysis, we will use Chi -square to test the difference between pioglitazone and placebo for the rate of no heavy drinking over the last 8 weeks (week 6-14) of the study. Hypotheses will also be tested across all time points to establish temporal patterns of group effects. For the continuous measures of alcohol use we will use mixed effects models if data residuals are normally distributed and generalized estimating equations (GEE) if the data are non-normally distributed (69, 70). Both are flexible regression methods for incomplete repeated measures data and allow continuous and categorical covariates, fixed and time-dependent covariates, and a specification of unstructured as well as structured covariance matrix. Secondary hypotheses will be evaluated using chi-square tests of proportions and logistic regression, with statistical significance criterion also set at $p < 0.05$ for categorical outcomes. Zero-inflated negative binomial analyses will be used to contrast the study groups on count variables if warranted by a high percentage of zero alcohol use days over the follow-up (71).

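### No rule gives a responder status to participants who withdraw with no heavy drinking day recorded in weeks 6–14, so the secondary responder test would most likely run on observed cases

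*Combined protocol and SAP*

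**What the plan says.** Section 4.4 defines the responder as a participant with no heavy drinking day over weeks 6–14, and names the test: "For the responder analysis, we will use Chi -square to test the difference between pioglitazone and placebo". For categorical secondary outcomes generally it adds: "Secondary hypotheses will be evaluated using chi-square tests of proportions and logistic regression". Mixed models and GEE are assigned to the continuous drinking measures; of these it says "Both are flexible regression methods for incomplete repeated measures data".

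Section 4.5 states "The primary intention to treat population will include all participants randomized", but sizes the responder comparison on 90 per group after attrition.

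Section 4.7 says that "all subjects randomized into two treatment groups will be included in the analysis", and of those who withdraw, "thereby their responses will be considered missing after withdrawal". It considers it plausible that "those with increase or no reduction in alcohol use may be more likely to drop out of the study". If dropout proves related to outcome, models for nonrandom dropout follow, with this limit: "These analyses will be carried out as the secondary analyses for hypothesis-generating purposes". A closing sentence says that the EM algorithm will let incomplete observations be included. It names no endpoint.

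Section 3.11 promises an effort to keep collecting data to the end of the study after assigned treatment is stopped.

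**The concern.** Responder status is one yes/no value per person. A chi-square or logistic regression uses only people who have that value. One recorded heavy drinking day in weeks 6–14 settles the matter as non-response, even if the person then leaves. The gap concerns those who leave before or during the window with no heavy day recorded in it. The plan includes them in principle, calls their later responses missing, and gives them no status.

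Section 4.4 chose this endpoint because of FDA guidance and its link to good clinical outcomes, so the absolute responder rate matters as well as the test. If people who are not improving leave more often, dropping the undetermined removes mostly non-responders and raises the reported rate. If that happens more in one arm, the comparison is biased too. With the rule open, the denominator could also be settled after the data are seen.

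**Working it through.** **1. The plan's own responder figure.** Section 4.5 gives 90 per group, a 22-point difference, OR 2.45, 80% power and p<.05. The base rate and sidedness are not stated. The pair 22 points and OR 2.45 implies about 39% versus 61%: (0.61/0.39)/(0.39/0.61) = 2.45. Two-sided 5% is assumed.
- Without continuity correction: n = [1.960·√(2·0.5·0.5) + 0.842·√(2·0.39·0.61)]² / 0.22² = 80 per group.
- With continuity correction: n = 89, which matches the stated 90.
- The same section assumes 20% attrition from 100 per group, and 100 × 0.8 = 80, not 90. Either number is a post-attrition count, not all randomised.

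**2. Who is undetermined.** Assume withdrawal is spread evenly over 14 weeks and heavy days are Poisson at r per week. Take r = 3.5 (baseline in the baclofen study, section 4.5) or r = 1.38 (six per month, the entry minimum in section 3.4).
- If drinking is known up to the day of leaving, the share is 6/14 + (1 − e^(−8r))/(14r) = 45% at r = 3.5 and 48% at r = 1.38.
- The TLFB is collected at visits, two weeks apart in this window (sections 3.1 and 3.9.1). Someone leaving between weeks 6 and 8 then has no window data unless reached later. The share becomes 8/14 + (2/14)(e^(−2r) + e^(−4r) + e^(−6r)) = 57% and 58%.

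So roughly half to 58% of such dropouts are undetermined. All of them is the upper bound.

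**3. Reported rate.** Take 100 per arm, a true rate of 25%, and 20% dropout only among non-responders.
- Half undetermined: 25/(100 − 10) = 27.8%.
- 58% undetermined: 25/(100 − 11.6) = 28.3%.
- All undetermined: 25/(100 − 20) = 31.3%.

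**4. Type I error of the observed-case test.** Simulation with no true effect, 100 per arm, and a two-sided chi-square without continuity correction unless stated. Each non-responder becomes undetermined with probability d·u/(1 − p), where d is the arm's dropout, u the undetermined share and p the true rate.

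| Dropout by arm | u | p = 25% | p = 39% |
|---|---|---|---|
| 20% / 20% | 0.5 or 1 | 5.0–5.1% | 5.0–5.1% |
| 18% / 22% | 0.5 | 5.1% | 5.2% |
| 18% / 22% | 1 | 5.6% | 6.2% |
| 14% / 24% | 0.5 | 5.7% | 6.3% |
| 14% / 24% | 0.57–0.58 | 5.9% | 6.7% |
| 14% / 24% | 1 | 8.3% | 11.9% |
| 14% / 24%, continuity-corrected | 0.5 | 3.9% | 4.5% |
| 14% / 24%, continuity-corrected | 1 | 5.9% | 8.9% |

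In section 4.6, 14% and 24% are the overall attrition rates of two earlier studies. Using them as two arms is an assumption. Counting the undetermined as non-responders gives 4.9–5.1% in the drinking-related cases run without continuity correction.

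**5. The choice can change a single result.** Illustrative counts: 16 placebo and 24 pioglitazone withdrawals, all undetermined, with 33/84 versus 46/76 responders among completers.
- Completers only: p = 0.007.
- Undetermined as non-responders (33/100 versus 46/100): p = 0.060.
- Undetermined as responders (49/100 versus 70/100): p = 0.0025.

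**The case against.** Section 4.7 is worded for all endpoints. It recognises informative dropout and offers EM estimation and nonrandom-dropout models. Section 4.5 says, straight after the responder power sentence, that mixed models and GEE use the whole intention-to-treat sample. A reader might infer from this review that the responder analysis cannot include everyone randomised, or that the plan prescribes a completers-only test. The documents support neither. Inclusion is possible once a rule is written, and the observed-case analysis is an inference about what would happen by default. What does stand is that none of these sentences supplies a status. The EM sentence assigns no value for a chi-square, section 4.4 ties mixed models and GEE to the continuous measures, and the nonrandom-dropout models are conditional and exploratory. The follow-up effort in section 3.11 may shrink the affected group but does not classify those who remain.

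It is also fair to say that the effect on the test is small. With equal dropout it is negligible. At the assumed 14% versus 24% split with half undetermined, a continuity correction, which section 4.5's 90 per group fits, brings the error below 5%.

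Counting the undetermined as non-responders is itself a choice with costs, and imputation is a defensible alternative. That is why the rule needs sensitivity analyses beside it.

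**Conclusion.** The gap is real, and the plan should close it. It concerns one secondary endpoint. The main consequence is overstated responder rates in both arms if dropout tracks drinking: about 28% for a true 25%, at most 31%, at 20% dropout. If dropout is unrelated to drinking, the direction can reverse. With half of the non-responder dropouts undetermined, the observed-case rate is 0.20/(0.20 + 0.75 × 0.90) = 22.9%, because the known non-responders stay in.

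The between-arm test suffers only if drinking-related dropout differs by arm, and clearly so only if the difference is large and nearly all dropouts are undetermined. All of this rests on assumed dropout patterns, evenly spread withdrawal and a base rate the plan does not state.

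A reader might take the point to undermine the primary outcome. It does not: heavy drinking days per week is analysed by repeated-measures methods that need no single status per person. That says only that this gap does not reach the primary outcome. Section 4.7's own doubt about data being missing at random is a separate question.

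**What to change.** Before unblinding, state in sections 4.4 and 4.7 that for the responder endpoint:
- the denominator is all randomised participants;
- all TLFB data obtained are used;
- anyone with a recorded heavy drinking day in weeks 6–14 is a non-responder;
- the remaining undetermined participants count as non-responders in the main analysis;
- their number is reported by arm;
- multiple-imputation and observed-case analyses are given as sensitivity analyses.

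Align the number per group in section 4.5 with this denominator.

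No new data collection is needed, but the rule has a price. Absolute responder rates fall. If dropout is equal at 20% and unrelated to drinking, power at 39% versus 61% falls from about 80% (completers only), or 82% (observed cases, half of non-responder dropouts undetermined), to 73%. At 25% versus 45%, also OR 2.45, it falls from 76% (completers only) to 72%. If unrelated dropout is unequal (14% versus 24%), non-responder counting gives a type I error of 7.4% at a true 25% and about 9.2% at 39%, against about 5.1% for completers only. If dropout is confined to non-responders, power at 39% versus 61% stays at the full-sample 89%.

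Separately, and at no cost, stratify the responder analysis by site or adjust for it, since site is the randomisation stratum (section 3.12). Use a Cochran–Mantel–Haenszel test or the logistic regression already named.
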